5.2.4 Proportion of Treatment Success at the End of Treatment

- The analysis presents the frequency and proportion of treatment success and failure in the investigational arm (Table 19).

Table 19. Proportion of Treatment Success at the End of Treatment

Investigational arm	
mITT analysis group	xx
Proportion of treatment success at the end of treatment, n (%)	xx (xx.xx)
Treatment failure, n (%)	xx (xx.xx)
PP analysis group	xx
Proportion of treatment success at the end of treatment, n (%)	xx (xx.xx)
Treatment failure, n (%)	xx (xx.xx)
Sub-group analysis	xx

1-1. Sputum smear positive ¹⁾	xx
mITT analysis group	xx
Proportion of treatment success at the end of treatment, n (%)	xx (xx.xx)
Treatment failure, n (%)	xx (xx.xx)
PP analysis group	xx
Proportion of treatment success at the end of treatment, n (%)	xx (xx.xx)
Treatment failure, n (%)	xx (xx.xx)
1-2. Sputum smear negative ²⁾	xx
mITT analysis group	xx
Proportion of treatment success at the end of treatment, n (%)	xx (xx.xx)
Treatment failure, n (%)	xx (xx.xx)
PP analysis group	xx
Proportion of treatment success at the end of treatment, n (%)	xx (xx.xx)
Treatment failure, n (%)	xx (xx.xx)

¹⁾Sputum smear positive at screening visit (visit1)

²⁾Sputum smear negative at screening visit (visit1)

5.2.5 Proportion of Relapse after Treatment Success

The analysis presents the frequency and proportion of relapse after treatment success in the investigational arm.

Table 20. Proportion of Relapse after Treatment Success

	Investigational Arm
mITT analysis group	xx

Treatment success	xx
Proportion of relapse after treatment success, n (%)	xx (xx.xx)
PP analysis group	xx
Treatment success	xx
Proportion of relapse after treatment success, n (%)	xx (xx.xx)
Sub-group analysis	xx
1-1. Sputum smear positive ¹⁾	xx
mITT analysis group	xx
Treatment success	xx
Proportion of relapse after treatment success, n (%)	xx (xx.xx)
PP analysis group	xx
Treatment success	xx
Proportion of relapse after treatment success, n (%)	xx (xx.xx)
1-2. Sputum smear negative ²⁾	xx
mITT analysis group	xx
Treatment success	xx
Proportion of relapse after treatment success, n (%)	xx (xx.xx)
PP analysis group	xx
Treatment success	xx
Proportion of relapse after treatment success, n (%)	xx (xx.xx)

¹⁾Sputum smear positive at screening visit (visit1)

²⁾Sputum smear negative at screening visit (visit1)

Treatment success rate at 24 months after the initiation of treatment, n (%)	xx (xx.xx)	xx (xx.xx)	xx (xx.xx)
Difference [95% CI]	xx.xx[xx.xx,∞] ¹⁾		
Treatment failure, n (%)	xx (xx.xx)	xx (xx.xx)	xx (xx.xx)
PP analysis group			
Not assessable ²⁾	xx	xx	xx
Treatment success rate at 24 months after the initiation of treatment, n (%)	xx (xx.xx)	xx (xx.xx)	xx (xx.xx)
Difference [95% CI]	xx.xx[xx.xx,∞] ¹⁾		
Treatment failure, n (%)	xx (xx.xx)	xx (xx.xx)	xx (xx.xx)
No pyrazinamide resistant			
mITT analysis group	xx	xx	xx

Not assessable ²⁾	xx	xx	xx
Treatment success rate at 24 months after the initiation of treatment, n (%)	xx (xx.xx)	xx (xx.xx)	xx (xx.xx)
Difference [95% CI]	xx.xx[xx.xx ∞] ¹⁾		
Treatment failure, n (%)	xx (xx.xx)	xx (xx.xx)	xx (xx.xx)
PP analysis group			
Not assessable ²⁾	xx	xx	xx
Treatment success rate at 24 months after the initiation of treatment, n (%)	xx (xx.xx)	xx (xx.xx)	xx (xx.xx)
Difference [95% CI]	xx.xx[xx.xx ∞] ¹⁾		
Treatment failure, n (%)	xx (xx.xx)	xx (xx.xx)	xx (xx.xx)

¹⁾If the lower limit of the confidence interval is larger than -10%, it proves that the efficacy of the study drug is inferior to the control drug.

²⁾The subjects judged to be "Not assessable are excluded from the assessment.

6. Safety Assessment Results

The safety analysis will be conducted for the mITT analysis group and the PP analysis group. Additionally, the safety analysis regarding the safety analysis group, that divides groups according to whether study drug delamanid or linezolid is administered, will be carried out for the subjects enrolled in this clinical trial and administered the study drug at least one time. The results of the safety evaluation will be summarized, focusing on adverse reactions and physical examinations, neurological examinations, chemistry, electrolyte, and complete blood count evaluated during this clinical trial period. The severity of adverse event will be evaluated based on CTCAE Version 4.0.

6.1 Adverse Events

The analysis presents the summary of the total number of adverse events, the number of subjects experiencing adverse events, and the serious adverse events, adverse event with grade 3-5 in this clinical trial (Table 23).

Table 23. Summary of Adverse Event Reported during Study Period

	Investigational Arm N=xx	Control Arm N=xx	Total N=xx
mITT			
Number of subjects showing adverse events, n (%)	xx (xx.xx)	xx (xx.xx)	xx (xx.xx)
95% confidence interval of adverse event rate	xx.xx±xx.xx	xx.xx±xx.xx	xx.xx±xx.xx
p-value ¹⁾	0.xxxx †† or **		
Number of adverse events, n	xx	xx	xx
Adverse drug reaction ²⁾			
Number of subjects showing adverse drug reaction, n (%)	xx (xx.xx)	xx (xx.xx)	xx (xx.xx)
p-value ³⁾	0.xxxx †† or **		
Number of adverse drug reaction, n	xx	xx	xx
Serious adverse events			

Number of subjects showing serious adverse events, n (%)	xx (xx.xx)	xx (xx.xx)	xx (xx.xx)
p-value ⁴⁾	0.xxxx †† or **		
Number of adverse events, n	xx	xx	xx
Adverse event of grade 3-5			
Number of subjects showing over grade 3 of adverse event, n (%)	xx (xx.xx)	xx (xx.xx)	xx (xx.xx)
p-value ⁵⁾	0.xxxx †† or **		
Number of grade 3 of adverse event, n	xx	xx	xx
Death			
Death, n (%)	xx (xx.xx)	xx (xx.xx)	xx (xx.xx)
p-value ⁶⁾	0.xxxx †† or **		
Seriousness			
Not serious, n	xx	xx	xx
Serious, n	xx	xx	xx
Severity			
Mild, n	xx	xx	xx
Moderate, n	xx	xx	xx
Severe, n	xx	xx	xx
life threatening or disabling, n	xx	xx	xx
Death, n	xx	xx	xx
Relation			
not related, n	xx	xx	xx
doubtful, n	xx	xx	xx
possible, n	xx	xx	xx
probable, n	xx	xx	xx

definite, n	xx	xx	xx
Action taken			
No action taken, n	xx	xx	xx
Dosage Adjustment of study drug, n	xx	xx	xx
Suspension of study drug, n	xx	xx	xx
Permanent termination of study drug, n	xx	xx	xx
Unknown, n	xx	xx	xx
Not applicable, n	xx	xx	xx
Dosage adjustment of TB medication other than the study drug, n	xx	xx	xx
Suspension of TB medication other than the study drug, n	xx	xx	xx
Permanent termination of TB medication other than the study drug, n	xx	xx	xx
Outcome			
Resolved, n	xx	xx	xx
Resolved with residual effect, n	xx	xx	xx
Ongoing, n	xx	xx	xx
Death, n	xx	xx	xx
Unknown, n	xx	xx	xx
PP	N=xx	N=xx	N=xx
Number of subjects showing adverse event, n (%)	xx (xx.xx)	xx (xx.xx)	xx (xx.xx)
95% confidence interval of adverse event rate	[xx.xx, xx.xx]	[xx.xx, xx.xx]	[xx.xx, xx.xx]
p-value ¹⁾	0.xxxx †† or **		xx
Number of adverse events, n	xx	xx	xx
Adverse drug reaction ²⁾			

Number of subjects showing adverse drug reaction, n (%)	xx (xx.xx)	xx (xx.xx)	xx (xx.xx)
p-value ³⁾	0.xxxx †† or **		xx
Number of adverse drug reaction, n	xx	xx	xx
Serious adverse event			
Number of subjects showing serious adverse events, n (%)	xx (xx.xx)	xx (xx.xx)	xx (xx.xx)
p-value ⁴⁾	0.xxxx †† or **		xx
Number of adverse events, n	xx	xx	xx
Adverse event of Grade 3-5			
Number of subjects showing over grade 3 of adverse event, n (%)	xx (xx.xx)	xx (xx.xx)	xx (xx.xx)
p-value ⁵⁾	0.xxxx †† or **		
Number of grade 3 of adverse event, n	xx	xx	xx
Death			
Death, n (%)	xx (xx.xx)	xx (xx.xx)	xx (xx.xx)
p-value ⁶⁾	0.xxxx †† or **		xx
Seriousness			
Not serious, n	xx	xx	xx
Serious, n	xx	xx	xx
Severity			
Mild, n	xx	xx	xx
Moderate, n	xx	xx	xx
Severe, n	xx	xx	xx
life threatening or disabling, n	xx	xx	xx
Death, n	xx	xx	xx
Relation			

not related, n	xx	xx	xx
doubtful, n	xx	xx	xx
possible, n	xx	xx	xx
probable, n	xx	xx	xx
definite, n	xx	xx	xx
Action taken			
No action taken, n	xx	xx	xx
Dosage Adjustment of study drug, n	xx	xx	xx
Suspension of study drug, n	xx	xx	xx
Permanent termination of study drug, n	xx	xx	xx
Unknown, n	xx	xx	xx
Not applicable, n	xx	xx	xx
Dosage adjustment of TB medication other than the study drug, n	xx	xx	xx
Suspension of TB medication other than the study drug, n	xx	xx	xx
Permanent termination of TB medication other than the study drug, n	xx	xx	xx
Outcome			
Resolved, n	xx	xx	xx
Resolved with residual effect, n	xx	xx	xx
Ongoing, n	xx	xx	xx
Death, n	xx	xx	xx
Unknown, n	xx	xx	xx
Safety	N=xx	N=xx	N=xx
Number of subjects showing adverse events, n (%)	xx (xx.xx)	xx (xx.xx)	xx (xx.xx)
95% confidence interval of adverse event rate	[xx.xx, xx.xx]	[xx.xx, xx.xx]	[xx.xx, xx.xx]

p-value ¹⁾	0.xxxx †† or **		
Number of adverse events, n	xx	xx	xx
Adverse drug reaction ²⁾			
Number of subjects showing adverse drug reaction, n (%)	xx (xx.xx)	xx (xx.xx)	xx (xx.xx)
p-value ³⁾	0.xxxx †† or **		
Number of adverse drug reaction, n	xx	xx	xx
Serious adverse events			
Number of subjects showing serious adverse events, n (%)	xx (xx.xx)	xx (xx.xx)	xx (xx.xx)
p-value ⁴⁾	0.xxxx †† or **		
Number of adverse events, n	xx	xx	xx
Adverse event of grade 3-5			
Number of subjects showing over grade 3 of adverse event, n (%)	xx (xx.xx)	xx (xx.xx)	xx (xx.xx)
p-value ⁵⁾	0.xxxx †† or **		
Number of grade 3 of adverse event, n	xx	xx	xx
Death			
Death, n (%)	xx (xx.xx)	xx (xx.xx)	xx (xx.xx)
p-value ⁶⁾	0.xxxx †† or **		
Seriousness			
Not serious, n	xx	xx	xx
Serious, n	xx	xx	xx
Severity			
Mild, n	xx	xx	xx
Moderate, n	xx	xx	xx
Severe, n	xx	xx	xx

life threatening or disabling, n	xx	xx	xx
Death, n	xx	xx	xx
Relation			
not related, n	xx	xx	xx
doubtful, n	xx	xx	xx
possible, n	xx	xx	xx
probable, n	xx	xx	xx
definite, n	xx	xx	xx
Action taken			
No action taken, n	xx	xx	xx
Dosage Adjustment of study drug, n	xx	xx	xx
Suspension of study drug, n	xx	xx	xx
Permanent termination of study drug, n	xx	xx	xx
Unknown, n	xx	xx	xx
Not applicable, n	xx	xx	xx
Dosage adjustment of TB medication other than the study drug, n	xx	xx	xx
Suspension of TB medication other than the study drug, n	xx	xx	xx
Permanent termination of TB medication other than the study drug, n	xx	xx	xx
Outcome			
Resolved, n	xx	xx	xx
Resolved with residual effect, n	xx	xx	xx
Ongoing, n	xx	xx	xx
Death, n	xx	xx	xx
Unknown, n	xx	xx	xx

†† p-value by the Chi-square test ** p-value by the Fisher's exact test

1) p-value for comparison test of adverse reaction incidence rate between groups

2) In the case of an adverse reaction related to the drug used, the contribution of the drug is Possible, Probable, or Definite

3) p-value for comparison test of the incidence of adverse drug reactions between groups

4) p-value for comparison test of incidence of serious adverse events between groups

5) p-value for the comparison test for the incidence of grade 3 adverse events between groups

6) p-value for intergroup mortality comparison test

The analysis presents the adverse events occurring for each body system during the clinical trial period. The body system is classified according to SOC (System Organ Class) and PT (Preferred Term) of the MedDRA system. The adverse events are summarized for each severity of the body system, relation, and body system (Tables 24, 25, and 26).

Table 24. Adverse Events for Each Body System

		Investigational Arm (N=xx)	Control Arm (N=xx)	Total (N=xx)
mITT				
System Organ Class	Preferred Term			
SOC1		X	X	X
	XXX	X	X	X
	XXX	X	X	X
SOC2		X	X	X
	XXX	X	X	X
	XXX	X	X	X
PP				
System Organ Class		Preferred Term		

SOC1	X	X	X	
	XXX	X	X	
	XXX	X	X	
SOC2	X	X	X	
	XXX	X	X	
	XXX	X	X	
Safety				
System Organ Class	Preferred Term			
SOC1	X	X	X	
	XXX	X	X	
	XXX	X	X	
SOC2	X	X	X	
	XXX	X	X	
	XXX	X	X	

Table 25. Adverse Events for Each Severity of Body System

System Organ Class	Preferred Term	Investigational Arm (N=xx)						Control Arm (N=xx)					
		Severity						Severity					
		1	2	3	4	5	>=3	1	2	3	4	5	>=3
mITT													
SOC1		X	X	X	X	X	X	X	X	X	X	X	X

	XXX	X	X	X	X	X	X	X	X	X	X	X	X
	XXX	X	X	X	X	X	X	X	X	X	X	X	X
SOC2	X	X	X	X	X	X	X	X	X	X	X	X	X
	XXX	X	X	X	X	X	X	X	X	X	X	X	X
	XXX	X	X	X	X	X	X	X	X	X	X	X	X
PP													
System Organ Class	Preferred Term												
SOC1		X	X	X	X	X	X	X	X	X	X	X	X
	XXX	X	X	X	X	X	X	X	X	X	X	X	X
	XXX	X	X	X	X	X	X	X	X	X	X	X	X
SOC2		X	X	X	X	X	X	X	X	X	X	X	X
	XXX	X	X	X	X	X	X	X	X	X	X	X	X
	XXX	X	X	X	X	X	X	X	X	X	X	X	X
Safety													
System Organ Class	Preferred Term												
SOC1		X	X	X	X	X	X	X	X	X	X	X	X
	XXX	X	X	X	X	X	X	X	X	X	X	X	X
	XXX	X	X	X	X	X	X	X	X	X	X	X	X
SOC2		X	X	X	X	X	X	X	X	X	X	X	X
	XXX	X	X	X	X	X	X	X	X	X	X	X	X
	XXX	X	X	X	X	X	X	X	X	X	X	X	X

Table 26. Adverse Events for Each Relation of Body System

		Investigational Arm (N=xx)						Control Arm (N=xx)					
		Relation						Relation					
		1	2	3	4	5	≥ 3	1	2	3	4	5	≥ 3
mITT													
System Organ Class	Preferred Term												
SOC1	X	X	X	X	X	X	X	X	X	X	X	X	X
XXX	X	X	X	X	X	X	X	X	X	X	X	X	X
XXX	X	X	X	X	X	X	X	X	X	X	X	X	X
SOC2	X	X	X	X	X	X	X	X	X	X	X	X	X
XXX	X	X	X	X	X	X	X	X	X	X	X	X	X
XXX	X	X	X	X	X	X	X	X	X	X	X	X	X
PP													
System Organ Class	Preferred Term												
SOC1	X	X	X	X	X	X	X	X	X	X	X	X	X
XXX	X	X	X	X	X	X	X	X	X	X	X	X	X
XXX	X	X	X	X	X	X	X	X	X	X	X	X	X
SOC2	X	X	X	X	X	X	X	X	X	X	X	X	X
XXX	X	X	X	X	X	X	X	X	X	X	X	X	X
XXX	X	X	X	X	X	X	X	X	X	X	X	X	X
Safety													
System Organ Class	Preferred Term												
SOC1	X	X	X	X	X	X	X	X	X	X	X	X	X
XXX	X	X	X	X	X	X	X	X	X	X	X	X	X
XXX	X	X	X	X	X	X	X	X	X	X	X	X	X

SOC2	X	X	X	X	X	X	X	X	X	X	X	X	X
XXX	X	X	X	X	X	X	X	X	X	X	X	X	X
XXX	X	X	X	X	X	X	X	X	X	X	X	X	X

The analysis summarizes in detail the serious adverse events reported during this clinical trial period (Table 27).

Table 27. Serious Adverse Event Evaluation Results

Subject No	Gender	Age	Adverse event name	Adverse event Onset date	Adverse event End date	Severity	Relation	Action taken	Outcome	Remarks
mITT										
Investigational Arm										
XX	XX		XX		XX		XX		XX	
XX	XX		XX		XX		XX		XX	
Control Group										
XX	XX		XX		XX		XX		XX	
XX	XX		XX		XX		XX		XX	
PP										
Investigational Arm										
XX	XX		XX		XX		XX		XX	
XX	XX		XX		XX		XX		XX	
Control Group										
XX	XX		XX		XX		XX		XX	

xx	xx	xx	xx	xx	xx	xx	xx	xx	xx
Safety									
Investigational arm									
xx	xx	xx	xx	xx	xx	xx	xx	xx	xx
xx	xx	xx	xx	xx	xx	xx	xx	xx	xx
Control arm									
xx	xx	xx	xx	xx	xx	xx	xx	xx	xx
xx	xx	xx	xx	xx	xx	xx	xx	xx	xx

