1.2. Difficulties with Treatment of MDR-TB

In order to treat MDR-TB, second-line anti-TB drugs including injectables must be used for 18-24 months, but the success rate of treatment has recently been reported as 83.7% in Korea (3). It is only 32.2% to 62.0% in other parts of the world (4,5). The WHO estimates the average treatment success rate of MDR-TB to be approximately 48% (Figure 1).

Furthermore, there is a report about frequent side effects of using these second-line drugs that commonly have side effects for usage over long periods of time. And 30% of the 818 MDR-TB patients, or 245 patients, had to stop use of drugs because of adverse drug reactions such as nausea/vomiting, diarrhea, joint pains, dizziness, hearing difficulty, headache, and sleep disorders. (6)

A considerable amount of money is used for treating MDR-TB patients. In the case of Korea, it costs 7-22 times more to treat MDR-TB patients than drug-susceptible TB patients. The expenses needed to treat MDR-TB are similar to that for treating malignant diseases, and thus depletes huge amounts of money.(7, Figure 2)

[figure not shown]

Figure 2 Comparison of the annual cost of multidrug-resistant tuberculosis (MDR-TB) with that of malignant disease in South Korea. All costs demonstrated in this figure are the National Health Insurance Programme-covered annual costs converted to 2004 US dollars.

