5.2. Primary Outcome

• Treatment success rate at 24 months after the initiation of treatment:

- ‘Cured’ and ‘treatment completed’ are defined as treatment success, and ‘culture’ defined below refers to results of liquid culture.
- Treatment failure, death, loss to follow-up, transfer out and relapse were excluded from treatment success.
- Definitions of treatment outcomes refer to 2014 WHO Guidelines (20). However, ‘stopping’ of drugs during treatment will not be considered as ‘drug change’ (Please see ‘6 Definitions’ in this protocol below.).

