3.5 Adherence Assessment

- The study coordinator checks the study drug adherence by comparing the drug package with residual pill count at each visit.

In the event that a scheduled visit is changed, the study coordinator checks administration status of the study drug and other medication during that period as well.

- Drug Adherence by each drug = (actual dosing day/ prescribed dosing day) * 100

- Final Adherence = Average value of medication adherence by each drug

In this case, the prescribed dosing day is defined as the sum of the prescribed dosing days for the entire period and the actual dosing day is defined as the total of the actual dosing days for the entire period, and the Final Adherence is defined as the average value of the Drug Adherence by each drug.

The Adherence to study drug and throughout the total treatment period of both arms is summarized with the final adherence and by each drug taken, with the mean, standard deviation, median and minimum and maximum value, and the final adherence will be compared between the two arms by conducting an independent t-test or Wilcoxon rank sum test.

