3.7 Safety Analysis

The safety analysis evaluates subjects enrolled in this clinical trial and administered the study drug at least one time.

1) Adverse Events

- The analysis obtains the 95% confidence interval of the proportion of the subjects who have experienced one or more adverse event within each arm and performs the Chi-Square Test or Fisher's Exact Test to compare the treatment groups.
- It compares the occurrence rate of adverse drug reactions of the two arms using the Chi-square test or Fisher's exact test.
- It summarizes the number of adverse events of each arm.
- It summaries the number of expressions of five items (seriousness, severity, relation, action taken, and outcome) for each arm.
- The classification of adverse events by body system is organized according to the SOC (System Organ Class) and PT (Preferred Term) of MedDRA system.
- It describes the details such as demographic information, event date, end date, severity, relation, action taken, and outcome for the subjects who reveal serious adverse events.

2) Physical/Neurological Examination Result

- For the results of the physical/neurological examination, the analysis presents the proportion of subjects who were normal in screening visit (Visit1) and changed to abnormal at the final visit.

3) Chemistry/Electrolyte/Complete Blood Count Result

- The analysis presents the proportion of subjects who showed the chemistry/electrolyte/complete blood count result of "Normal" or "Abnormal NCS" at the baseline visit (Visit2) and changed to "Abnormal CS" at the final visit.

4) Concomitant Medication

- The analysis classifies the concomitant medication using the ATC (Anatomical Therapeutic Chemical)

Code presents it for each arm.

4. Subjects

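### Table 23 counts drugs stopped for adverse events as events split by drug type, so no planned table gives the share of participants who permanently stopped a TB drug for an adverse event

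*Combined protocol and SAP*

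**What the plan says.** SAP 3.7 sets the unit for the action-taken summary: "It summaries the number of expressions of five items (seriousness, severity, relation, action taken, and outcome) for each arm". Table 23 (SAP 6.1) follows it. The rows for participants with any adverse event, an adverse drug reaction, a serious event or a grade 3–5 event, for example "Number of subjects showing adverse drug reaction, n", carry a percentage and a Chi-square or Fisher p-value. The action-taken rows carry a number only. Permanent stops appear there twice, as "Permanent termination of study drug, n" and as "Permanent termination of TB medication other than the study drug, n", and the same layout is used in the mITT, per-protocol and safety blocks.

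Table 23 does not define study drug. SAP 6 describes the "safety analysis group, that divides groups according to whether study drug delamanid or linezolid is administered", and SAP 3.1 defines the safety set in the same terms.

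Three other places bear on the point:

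- SAP 3.5 on adherence: "Drug Adherence by each drug = (actual dosing day/ prescribed dosing day) * 100".
- Protocol 5.2: stopping "of drugs during treatment will not be considered as" a drug change when outcomes are classified.
- Protocol 1.2, as background to the trial: "30% of the 818 MDR-TB patients, or 245 patients, had to stop use of drugs because of adverse drug reactions".

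**The concern.** Tolerability is part of the case for the new regimen, and the protocol's own background figure on stopping drugs is a share of patients. The planned rows do not yield such a share. A tally of events does not fix the number of people behind it, and two rows that may contain the same person cannot be added to give one.

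The split by drug type adds a second problem. If study drug means delamanid or linezolid, a reader who compares the two columns of the study-drug row sees a difference that largely reflects who was given those drugs. Levofloxacin and pyrazinamide stops in the investigational arm fall in the other row, together with nearly all stops in the control arm.

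The hypothesis concerns a four-drug regimen, yet stopping a drug does not by itself make a participant a treatment failure. How many investigational successes finished on all four drugs is useful for reading the primary result, and no table is planned to show it.

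**Working it through.** **1. Unit of the rows.** SAP 3.7 asks for the number of occurrences of each item. Table 23 reports serious events both as participants with a percentage and as an event count. It thus separates the two units, but gives drug stops only as events.

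**2. Meaning of study drug.** This is inferred. For the narrow meaning (delamanid or linezolid):
- the SAP 3.1 safety definition and SAP 6;
- Protocol 5.1.1, which lists only those two under study drug;
- the contrast in Table 23 with TB medication other than the study drug;
- Table 1, which removes control participants given study drug between mITT and PP. That step makes no sense if the term covers every TB drug.

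Against it: the mITT definition requires at least one dose of study drug, and under the narrow meaning that would remove most controls. The term is used in both senses. The narrow one fits Table 23.

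**3. The study-drug row, block by block, on the narrow meaning.**
- mITT: every investigational participant is assigned both drugs. Protocol 5.1.2 allows them in control only with injectable resistance or after adverse reactions to other drugs.
- PP: control participants given study drug are excluded (SAP 3.1, Table 1), so the control count is zero whatever the tolerability. This needs no numerical assumption.
- Safety: if grouped by administration, as SAP 6 says, the unexposed group's count is also zero by construction.

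**4. Other outputs.**
- Table 1 counts withdrawals and treatment failures, neither specific to adverse events nor by drug.
- Table 14 gives adherence by drug, without a reason for stopping.
- Table 27 lists action taken by subject, for serious events only.
- The 80% rule for the PP set counts weeks of treatment, not drugs.

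**5. Background figure.** 245/818 = 29.95%, which reproduces the stated 30%.

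**6. From events to participants (illustration).** Assume 30 permanent-termination events in an arm of 102, the planned enrolment per arm in Protocol 10.1:
- one event each: 30/102 = 29.4%;
- two each: 15/102 = 14.7%;
- four each: 30/4 = 7.5, so at least 8 people, 8/102 = 7.8%.

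**7. What a participant-level row would deliver.** Assume p = 245/818 in both arms. The 95% half-width is 1.96 × √(p(1−p)/n) for one arm and 1.96 × √(2p(1−p)/n) for the difference.

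| n per arm | One arm | Difference |
|---|---|---|
| 48 (evaluable) | ±13.0 points | ±18.3 points |
| 102 (enrolled) | ±8.9 points | ±12.6 points |

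The comparison would be imprecise but reportable.

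**The case against.** The strongest reply is that this is a missing tabulation, not missing data. Action taken is recorded per adverse event, so the participant count can be derived later. Stopping a drug is not a declared endpoint. The declared safety outcome, grade 3 and higher events, is already compared by participant. The 30% comes from another cohort and is background, not a planned comparator. Protocol 11.2 asks that symptoms be recorded under one diagnosis where possible, which limits how far events exceed participants. The safety block lets study-drug actions be set against the number exposed. A between-arm interval would also compare four drugs over 9 or 12 months with about five over 20 to 24 months.

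Most of this stands, and it sets the weight of the point. It does not supply the missing row. The exposure grouping still counts events, and its unexposed column is empty by construction. The SAP states that it exists to prevent unplanned analysis, so the row is better specified now.

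A reader might go further and infer any of the following:

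- **That Table 14 would show full adherence after a drug is permanently stopped.** SAP 3.5 sums prescribed days over the entire period and does not say whether days after a stop still count as prescribed. If they do, adherence falls.
- **That the action-taken rows are the sole record of stops.** Table 27 lists them for serious events.
- **That the arms differ by some particular factor in the study-drug row.** Any such figure needs a stopping risk and a control exposure rate, and the documents give neither.
- **That per-drug stopping rates can certainly be derived.** The action-taken categories do not name the drug, and the adherence records are not shown to hold a reason.
- **That the non-inferiority conclusion is undermined.** Nothing here touches it.

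**Conclusion.** The point holds as a gap in planned safety reporting. The participant-level share of permanent stops for adverse events is not planned to be reported or compared, and the study-drug row is not comparable between arms. The first part follows from the wording of SAP 3.7 and the layout of Table 23. The second rests on reading study drug as delamanid or linezolid, which is well supported but inferred.

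The numerical size is illustrative only, since the event tally, the events per person and the 30% applied to both arms are assumptions. The improvement is descriptive and modest, and worth making because it costs little.

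**What to change.** Keep the event rows in Table 23 and define study drug in a footnote. Add one row by randomised arm, each participant counted once, n (%) with the difference and 95% CI: permanent termination of at least one anti-TB drug, study drug or other, because of an adverse event. A footnote should say that regimens and treatment durations differ between arms.

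Where the dosing records identify both the drug and the reason, add for the investigational arm:
- descriptive rows for linezolid, delamanid, levofloxacin and pyrazinamide separately;
- the number of 24-month successes who ended treatment on all four drugs.

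The core row can be derived from the action-taken entries already recorded, so it costs SAP wording and table programming. The per-drug rows depend on what the records hold, which should be checked before they are promised. The small downside is that the regimen's tolerability may look less favourable than in an event tally.
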